6.2 Blinding

The patient, the investigators performing study-specific assessments, and the sponsor will all be blinded to the intervention allocation, until all data processing is finished. However, one anesthetist performing the intervention will be unblinded to the allocation.

Sealed coding-envelopes containing data on randomization are stored in a locked cabinet at the Dept. of Anesthesiology, Hvidovre Hospital. If an unblinding of a randomized patient is deemed necessary by the attending physician, to secure health and patient-safety, unblinding will be made by opening the sealed patient-specific randomization envelope, containing set patient's allocation. The on-site investigator can always also be contacted to assist in unblinding and guidance. In case of unblinding, the reason for unblinding is noted, dated, and signed by the investigator in the specific patient CRF.

6.3 Procedures in case of emergency

The investigator will ensure that emergency procedures and the necessary expertise will be available for the patient during the study.

7. Statistics

7.1 Power calculation

Data from our previous study showed that pain during a 5-meter walk test at 24 h was the best predictor of cumulated pain on days 2-7 after TKA surgery [[name] et al. – IN PREPARATION]. With the optimal cut-off of VAS ≥ 45 , the mean (SD) cumulated pain during a 5-meter walk test on days 2-7 was 390 (208). A 50 % reduction in cumulated mean VAS upon mobilization days 2-7 postoperatively is clinically relevant. In a two-sided superiority design with a level of significance of 0.05 and a power of 80% we need two groups of 18 patients each. Assuming a small number of dropouts, 22 patients will be included in each of the two groups resulting in inclusion of 44 patients in total.

7.2 Data analysis

All participants who meet the inclusion criteria and undergo randomization will be included in the intention-to-treat (ITT) population. The per-protocol (PP) population is defined as the group of patients who are randomized, receive the treatment to which they were randomly assigned, and complete their assessments without any major protocol deviations. The primary and secondary outcome analyses will each be performed for the ITT and PP populations. The primary endpoint along with other continuous data will be tested using independent samples t-test or Mann-Whitney U test as appropriate. The secondary outcomes will also be analyzed relative to the pain relief during the initial LA injection in the cryo group versus the remaining patients from both groups. A P -value < 0.05 is considered significant. Dichotomized data will be tested using Chi-square or Pearson's exact test. Uni- and/or multivariate analysis, where appropriate, will be made to test for independent variables. Missing values will be accounted for in the final statistical plan. Statistical calculations will be made using either R statistical software (Open source) or SPSS statistics (IBM, New York, USA).

The study will be registered at Clinicaltrials.org and will include a complete statistical analysis plan submitted to publication.

8. Study plan

A general layout of the study is provided in Appendix 1. In the outpatient clinic, the screening procedure will be performed among patients planned for TKA by the surgeons. Patients will be asked by orthopedic staff whether they may be contacted regarding the research project. The research staff will then contact potential patients either in person or via telephone. The written study information will be explained – either at the outpatient clinic or via telephone by the investigator.

All patients receive both spoken and written information. Information is given in a separate closed room without interruptions. All patients are given the chance of an additional meeting with the chance of bringing a relative. All patients must give a signed informed consent on paper prior to inclusion to participate in the study. The patient will sign the consent form on day 1 after surgery.

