The effect of cryoneurolysis on knee pain has been documented in a few studies. A randomized, double-blind, sham-controlled trial found that cryoneurolysis reduced symptoms of knee osteoarthritis for up to 150 days [18]. A retrospective chart-review of 100 patients undergoing TKA found that cryoneurolysis significantly lowered LOS, reduced opioid consumption until 12 weeks after surgery, and reduced pain at the 2- and 6-weeks follow-up [19]. Another retrospective analysis in 267 patients undergoing TKA found a comparable reduction in opioid requirements, pain, and LOS in patients treated with cryoneurolysis compared with historic controls [20]. A recent RCT comparing cryoneurolysis to standard of care in 124 patients undergoing TKA found that cryoneurolysis reduced opioid consumption at 72 h, 6 weeks and 12-week follow-ups [21].

Although these findings are promising, cryoneurolysis is expensive and comprehensive, and might not be relevant in all patients receiving multimodal analgesia with COX-2 inhibitors, paracetamol, local infiltration analgesia, and high-dose steroid in a fully implemented enhanced recovery program [22, 23]. Several risk factors have been associated with a high pain response including age, gender, preoperative pain, psychological profile, and quantitative sensory testing (QST) [24-26]. However, when including postoperative pain in

the prediction of acute pain, movement-evoked pain 24 h postoperatively is the best predictor for pain the week following surgery [[name] et al. – IN PREPARATION].

Using postoperative pain 24 h after surgery as a predictor of a sustained high pain response, we hypothesized that postoperative cryoanalgesia compared to a local anesthesia (LA) block with sham cryo treatment would reduce pain in patients with moderate to severe pain following TKA 2-7 days after surgery.

2. Aim

To compare the effect of postoperative cryoanalgesia with a sham treatment consisting of LA block only on postoperative pain in the first week after surgery in TKA patients with moderate to severe pain on the first postoperative day.

3. Outcomes

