5.1 Inclusion criteria

- Age ≥ 18
- Primary unilateral TKA
- Ability to participate in the study (understand written and spoken Danish language, self-reported pain and satisfaction)
- Signed written informed consent form
- Pain (VAS 0-100 mm) ≥ 45 during a 5-meter walk test at 24 h (20-28h) postoperatively

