6.1 Randomization

Using <https://www.sealedenvelope.com/>, a randomization will be carried out using 2:2 block-randomization, half of which will be allocated to the sham-group and the other half to the cryo-group.

It is not possible to perform the cryoneurolysis while being blinded. Thus, the anesthetist performing the intervention will be unblinded. However, the patient and all personnel involved in study-specific assessments will be blinded to the allocation.

Group 1: sham-group	Postoperative ultrasound guided nerve block with LA followed by sham cryoneurolysis of the superficial genicular nerves.
Group 2: cryo-group	Postoperative ultrasound and guided nerve block followed by cryoneurolysis of the superficial genicular nerves.

<https://www.sealedenvelope.com/> will generate unique randomization codes to be imported to REDCap. Two lists containing the unique randomization codes will be made and stored at the Dept. of Anesthesiology, Hvidovre Hospital.

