8.2 Intervention

The intervention will take place after the inclusion at 20-32 h after TKA surgery. The procedure will be performed at the Dept. of Anesthesiology.

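### The primary test leaves out the 24-hour walk-test VAS, the protocol's own best predictor of the outcome; the test is valid but gives up precision and protection against chance imbalance

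*Combined protocol and SAP*

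**What the plan says.** - **Primary test (section 7.2).** "The primary endpoint along with other continuous data will be tested using independent samples t-test or Mann-Whitney U test as appropriate". No covariate is named.
- **Other modelling text (section 7.2).** "Uni- and/or multivariate analysis, where appropriate, will be made to test for independent variables". This is not tied to the primary endpoint and names no variable. A complete analysis plan is promised; the only item expressly deferred to it is missing data: "Missing values will be accounted for in the final statistical plan".
- **Prognostic value.** Section 7.1 says that "pain during a 5-meter walk test at 24 h was the best predictor of cumulated pain on days 2-7 after TKA surgery". Section 1.1 says that "movement-evoked pain 24 h postoperatively is the best predictor for pain the week following surgery".
- **Availability.** Section 5.1 requires a VAS of at least 45 "during a 5-meter walk test at 24 h (20-28h) postoperatively". Section 8.2 places treatment later: "The intervention will take place after the inclusion at 20-32 h after TKA surgery". The score is therefore a true pre-treatment measurement, present in every correctly enrolled patient.
- **Allocation (section 6.1).** "a randomization will be carried out using 2:2 block-randomization". No stratification factor is given.

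**The concern.** The protocol selects patients on the score it regards as most informative about the outcome, then sets that score aside in the primary test. Neither the randomization nor the analysis deals with a chance difference between arms in 24-hour pain. With 22 patients per arm such differences are not rare, and the primary estimate would carry part of them.

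Two things are at stake. The first is the width of the confidence interval, if the score still predicts the outcome within the enrolled range. The second is how a trial with visibly unequal baseline pain would be read. If adjustment is chosen only after the data are seen, the adjusted result loses much of its authority.

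**Working it through.** **Inputs from the documents.** Mean 390 and SD 208 for cumulated walk-test VAS on days 2-7 in patients with VAS of at least 45; a 50% reduction, so a difference of 195; two-sided alpha 0.05; 80% power; 18 per group, raised to 22 for dropout (all section 7.1).

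**Assumed input.** r, the correlation between the 24-hour score and the outcome among enrolled patients. The documents give no value, so it is varied from 0 to 0.5.

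**1. The plan's own figure.** Standardized difference = 195/208 = 0.9375. n per group = 2 × (1.960 + 0.842)² / 0.9375² = 17.9, rounded up to 18. This reproduces the protocol. With the noncentral t distribution, unadjusted power is 78.0% at 18 per arm and 85.9% at 22.

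**2. Unadjusted precision at 22 per arm.** Standard error = 208 × √(2/22) = 62.7. The 95% CI half-width is 126.6 points.

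**3. Precision with ANCOVA.** Adjustment multiplies the residual variance by (1 − r²). Two costs offset this: one degree of freedom (2n − 3 instead of 2n − 2), and an expected variance penalty for random covariate imbalance of 1 + 1/(2n − 4), which is 1.025 at n = 22 and 1.031 at n = 18. Both are counted below. The equivalent number of patients is 44 × [1/((1 − r²) × 1.025) − 1].

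| r | Net variance ratio, 22/arm | CI half-width, 22/arm | Equivalent extra patients (of 44) | Power, 22/arm | Power, 18/arm |
|---|---|---|---|---|---|
| unadjusted | 1.000 | 126.6 | – | 85.9% | 78.0% |
| 0 | 1.025 | 128.2 | −1.1 | 85.0% | 76.7% |
| 0.1 | 1.015 | 127.6 | −0.6 | 85.4% | 77.1% |
| 0.2 | 0.984 | 125.6 | 0.7 | 86.4% | 78.3% |
| 0.3 | 0.933 | 122.3 | 3.2 | 88.2% | 80.5% |
| 0.4 | 0.861 | 117.5 | 7.1 | 90.5% | 83.5% |
| 0.5 | 0.769 | 111.0 | 13.2 | 93.3% | 87.4% |

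Break-even is at r of about 0.16 with 22 per arm and 0.18 with 18. The lost degree of freedom alone costs less than 0.1 percentage point of power at 22 per arm; nearly all of the loss at r = 0 is the imbalance penalty.

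**4. Chance imbalance at 22 per arm.** The between-arm difference in the 24-hour score has standard deviation √(2/22) = 0.30 SD. The probability that it reaches 0.5 SD in either direction is 2 × [1 − Φ(0.5/0.30)] = 9.7%, using the unrounded 0.3015. An imbalance of exactly 0.5 SD shifts the unadjusted estimate by r × 0.5 × 208, and larger imbalances shift it more.

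| r | Shift at 0.5 SD (points) | As a fraction of the standard error (62.7) |
|---|---|---|
| 0.2 | 21 | 0.33 |
| 0.3 | 31 | 0.50 |
| 0.4 | 42 | 0.66 |
| 0.5 | 52 | 0.83 |

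**5. Error rates.** These come from 400,000 simulated trials per value of r (bivariate normal data, no treatment effect, 22 per arm). Over all trials, both the t-test and ANCOVA reject in 5%. Within trials with an imbalance of at least 0.5 SD, the t-test rejects in about 6.6%, 8.4%, 10.8% and 14.3% for r of 0.2, 0.3, 0.4 and 0.5, while ANCOVA stays near 5%. In the remaining 90% of trials the t-test rejects slightly too rarely, in about 4.8% down to 4.0%.

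**The case against.** The strongest reply is that nothing is wrong. An unadjusted comparison in a randomized trial is legitimate, its standard error already allows for chance imbalance, and its overall error rate is 5%. That stands, and the point does not claim otherwise.

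The second reply concerns the benefit. Being the best predictor is a ranking, not a strength, and it rests on an unpublished study. Enrolling only patients with VAS of at least 45 narrows the score's range and can be expected to lower r. The SD of 208 already belongs to that restricted group, so eligibility has used part of the predictor. This also stands: at r = 0.1 adjustment loses half a point of power at 22 per arm, and at r = 0.2 the gain is under one patient. The downside is small, however: at most 0.9 point at 22 per arm and 1.3 at 18, against gains of 7.4 and 9.4 points at r = 0.5.

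Third, the multivariate sentence and the promised plan leave room for adjustment, and a baseline table would show any imbalance. Both are true. But a clause that names no variable and no endpoint does not prespecify an adjusted primary analysis. A baseline table shows an imbalance without removing it from the primary estimate.

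**Conclusion.** The point holds as an improvement that should be made, not as an error. The primary test is valid, the sample size reproduces, and N need not change. What is lost is precision and protection in an unlucky allocation. Net of all costs at 22 per arm, the effect on power runs from a loss of 0.9 point at r = 0 to gains of 0.5, 2.3, 4.6 and 7.4 points at r = 0.2, 0.3, 0.4 and 0.5. In roughly one trial in ten, baseline imbalance would move the unadjusted estimate by at least a third to four fifths of a standard error for r between 0.2 and 0.5.

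The textual facts are certain. The size of the gain is not: it rests on an assumed r and on approximately normal data with a linear relation between score and outcome. The sponsor could estimate r from the patients with VAS of at least 45 in its own preceding study.

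**What to change.** In section 7.2 and the final analysis plan, before unblinding:

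- Make the primary analysis a linear regression (ANCOVA) of cumulated walk-test VAS on days 2-7 on treatment arm and the 24-hour walk-test VAS as a continuous covariate, in the ITT population.
- Report the adjusted mean difference with its 95% CI, with a robust or bootstrap interval if residuals are skewed.
- Identify the covariate as the 20-28 hour inclusion rating. Treatment may follow as late as 32 hours (section 8.2), and section 8.3 mentions a rating before the intervention that may be a different measurement.
- Apply the missing-data rule, still to be written, within this same model.
- Keep the unadjusted t-test or Mann-Whitney test, and the per-protocol analysis, as sensitivity analyses.

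The cost is a change of wording. No data, visits or patients are added.

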3.2 Secondary outcome

- Pain (VAS 0-100) during rest and during 5-meter walk test at the 2 weeks, 4 weeks, 12 weeks, and 24 weeks follow-up
- Pain relief immediately following blockade evaluated as Δ VAS 0-100 during a 5-meter walk test before and after the blockade
- Cumulated pain at rest and during night from days 2-7
- Quality of sleep and nausea postoperatively from days 2-7
- Cumulative use of rescue-analgesics from days 2-7, and at 2 weeks, 4 weeks, 12 weeks, and 24 weeks follow-up
- Oxford knee score at 12 weeks
- LOS in hospital, and reasons for prolonged stay (>1 postoperative day) registered as “Why still in hospital”
- Reasons for re-admissions within 12 weeks
- Morbidity and mortality (4-, 12-, and 24 weeks follow-up by Electronic Patient Journal (EPJ) or telephone)

4. Study design

Randomized, participant- and observer-masked, sham-controlled trial.

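### Section 7.2 calls any secondary result with P < 0.05 significant, across about 19 to 24 unadjusted tests per population, with no hierarchy or supportive label

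*Combined protocol and SAP*

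**What the plan says.** Section 3.1 names one primary outcome, cumulated walking pain on days 2-7, and section 7.1 powers the trial on it alone. Section 3.2 lists the secondary outcomes without ranking them. Several are repeated over time, for example "Pain (VAS 0-100) during rest and during 5-meter walk test at the 2 weeks, 4 weeks, 12 weeks, and 24 weeks follow-up" and "Cumulative use of rescue-analgesics from days 2-7, and at 2 weeks, 4 weeks, 12 weeks, and 24 weeks follow-up".

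Section 7.2 gives the analysis. For continuous outcomes: "The primary endpoint along with other continuous data will be tested using independent samples t-test or Mann-Whitney U test as appropriate". For populations: "The primary and secondary outcome analyses will each be performed for the ITT and PP populations". For the threshold: "A P -value < 0.05 is considered significant". It also plans a further pass through the secondary outcomes according to pain relief after the initial local anaesthetic injection.

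The section mentions univariate or multivariate analysis to test for independent variables, but specifies no longitudinal model. It leaves missing values to a final statistical plan and promises a complete SAP. It does not say that multiplicity or the choice of test will be revisited there.

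**The concern.** The threshold in 7.2 is a stated rule. It lets any secondary comparison, at any visit and in either population, be reported as significant in its own right. With many comparisons and 44 patients, some will cross 0.05 by chance. If the primary result is null, a difference in, say, rest pain at one follow-up call could be reported as a significant effect of cryoneurolysis, and nothing in the plan would mark it as weaker evidence. Section 11.2 looks ahead to shorter stay, fewer complications, lower opioid intake and guideline changes, so such findings would attract attention.

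A second, smaller matter is that follow-up pain is one course over time, measured four times in the same patients. Two-sample tests at each visit treat it as four unrelated questions per measure.

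**Working it through.** **The plan's own figure.** Section 7.1 uses a mean of 390, an SD of 208 and a 50% reduction, so the difference is 0.5 × 390 = 195. By the normal formula, n = 2 × [(1.960 + 0.842) × 208 / 195]² = 17.9, or 18 per group, as stated. The two-sided 5% level is thus allotted to the primary outcome. The plan gives no error rate for the secondary outcomes.

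**Number of tests.** The documents state no count. This one is inferred by applying 7.2 to 3.2:

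| Secondary outcome | Tests |
|---|---|
| Pain at rest and walking, 4 visits | 2 × 4 = 8 |
| Pain relief after blockade | 1 |
| Cumulated rest and night pain | 2 |
| Sleep quality, nausea | 2 |
| Rescue analgesics, days 2-7 and 4 visits | 5 |
| Oxford knee score | 1 |
| Length of stay | 1 |
| Re-admission | 1 |
| Morbidity and mortality (combined), 3 visits | 3 |
| Total | 24 |

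Five of these may not act as ordinary 5% tests of cryoneurolysis: re-admission (1), which is listed as reasons; morbidity and mortality (3), which are probably sparse; and pain relief after blockade (1), which 8.2.2 places before freezing. Without them, 24 − 5 = 19. The PP repeat and the pass by local anaesthetic response come on top and are not counted.

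**Chance of at least one false positive, no effect on any outcome.** If the tests are independent, it is 1 − 0.95^k. With a common correlation r between the test statistics (assumption, range 0 to 0.7), it is 1 − ∫ φ(u) [Φ((1.96 − √r u)/√(1 − r)) − Φ((−1.96 − √r u)/√(1 − r))]^k du, integrated numerically.

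| Tests (k) | r = 0 | r = 0.3 | r = 0.5 | r = 0.7 |
|---|---|---|---|---|
| 24 | 70.8% | 59.5% | 45.8% | 31.1% |
| 19 | 62.3% | 52.5% | 40.9% | 28.3% |
| 8 (follow-up pain only) | 33.7% | 30.0% | 25.0% | 19.1% |

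The expected number of false positives is 24 × 0.05 = 1.2, or 19 × 0.05 = 0.95, whatever the correlation. The chance falls below 50% at a common correlation of about 0.44 for 24 tests and about 0.35 for 19. With higher correlation within an outcome domain than between domains, 24 tests give 66.9% (0.3 within, 0.1 between), 54.8% (0.7, 0.2) and 42.3% (0.7, 0.5).

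**Would a longitudinal model alone solve this?** No. One test per pain measure would cut 8 tests to 2 and the total to 24 − 8 + 2 = 18. The chance would still be 60.3% if independent and 39.8% at r = 0.5. The labelling has to change as well.

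**Precision at a visit with missed calls.** If a fraction m misses the last visit and an earlier visit correlates r with it, the variance under a joint model relative to a complete-case test is about 1 − r²m. With m = 0.1 and r = 0.5 this is 1 − 0.25 × 0.1 = 0.975. With m = 0.2 and r = 0.7 it is 1 − 0.49 × 0.2 = 0.902. The gain is therefore about 2% to 10%. Both m and r are assumptions; the documents give neither.

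**The case against.** **The trial already has a hierarchy of sorts.** One outcome is primary, it alone is powered, and the rest are called secondary. Section 19 commits to publishing negative and inconclusive results. This stands, and the secondary tests leave the primary error rate untouched. But the word secondary sits beside a rule that calls every P < 0.05 significant, and nothing says that secondary results cannot carry a claim.

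**The count and the error rate can be overstated.** This stands. Some items are descriptive, and rare binary events are tested well below 5%: with 22 per arm, the exact test has a true size of about 0.3% at an assumed 5% event rate and 1.4% at 10%. Repeated pain scores are likely to be well correlated. A reader might infer that a false secondary claim is more likely than not. That holds only below a common correlation of about 0.35 to 0.44, and the documents give no correlation.

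**Missing data are deferred.** A reader might infer from the two-sample tests that data from missed calls are wasted. The documents do not support this: 7.2 leaves missing values to a final plan, and a patient's other visits still enter their own tests. What can be said is that the stated tests do not use other visits to inform a missed one.

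**Separate visit contrasts are defensible.** Section 1.1 expects the block to resolve within weeks to months, so one overall arm test over 2 to 24 weeks could average an early effect with none. This stands. It argues against an overall test, but a joint model that reports each visit's difference avoids the problem.

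**Conclusion.** The point holds as a matter of labelling and analysis of secondary outcomes. Section 7.2 applies an unadjusted threshold to about 19 to 24 secondary tests per population, in both ITT and PP, without a hierarchy or supportive label. If there is no effect on any outcome, the chance of at least one false secondary claim is roughly 30% to 70%. The range follows the test count and a common correlation assumed between 0 and 0.7; 71% is the upper end, reached only with 24 independent tests each at full 5% size. Even the lower end is well above 5%.

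The case for a joint model of follow-up pain is secondary. It gives one coherent analysis per measure and, under assumed missed-call rates, a variance gain of about 2% to 10%.

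**What to change.** Put this in 7.2 and carry it into the promised SAP:

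*Only the primary outcome in the ITT population supports a claim of statistical significance. All secondary outcomes and PP analyses are supportive and are reported as estimates with 95% confidence intervals. Pain at rest and pain on walking at 2, 4, 12 and 24 weeks are each analysed with one mixed model for repeated measures (arm, visit, arm × visit, unstructured covariance, Kenward-Roger degrees of freedom), reporting visit-specific differences with 95% confidence intervals. If residuals are clearly skewed, a Mann-Whitney test per visit is a sensitivity analysis.*

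No overall arm test across visits should be added. It would sit badly with reserving significance for the primary outcome and could hide an early effect. The pass by local anaesthetic response concerns secondary outcomes, so it falls under the same supportive label.

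The cost is SAP wording and slightly more analysis. Patients, visits and sample size do not change. The downside is that fewer secondary results can be called significant.

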8.2.2 Procedure technique

Cryo-group:

The patient is placed in a supine position with a sheet between the upper and lower part of the body, thus blinding the patient from the intervention allocation. The procedure is performed using a linear array ultrasound probe. Local anesthesia is injected in the skin. The superficial genicular nerves, more specifically the ISN and the AFCN, are visualized. A nerve stimulator (Stimuplex HNS 12, B Braun, Melsungen, Germany) is used to verify the visualized nerves., 2-3 ml of ropivacaine 5 mg/ml is injected around the nerves. After 5-15 minutes the effect is evaluated by assessing pain in the surgical area and asking the patient whether there is a pain relief. Following this evaluation, cryoneurolysis (Cryo-S, Metrum Cryoflex, Blizne Laszczynskiego, Poland) is performed unilaterally along a treatment line, the location of which was guided by visualization and palpation of anatomic landmarks. The ISN treatment line is located along the line that connects a point located 5 cm medial to the lower pole of the patella and a point located 5 cm medial to the tibial tubercle. The AFCN treatment line is located at one-third the length of the distance from the center of the patella to the top of the femur, with a width equal to the width of the patella.

Sham-group:

The exact same procedure as in the cryo-group is performed, except that the nerves are not frozen with the cryoneurolysis apparatus. Sound effects from the machine are replicated to give the patient the same experience as in the active intervention group.

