8.3 Study specific

Pain is rated by the patient before the intervention, after the initial LA injection, at home on days 2-7 and at the 2-, 4-, 12-, and 24 weeks follow-up via telephone.

A Visual Analog Scale (VAS 0-100) is used. On days 1-7 patients mark their pain in the electronic CRF twice a day (Appendix 5). If the patient is not able to complete the ratings electronically, a physical pain diary will be provided. Pain is rated by the patient at rest, during a 5-meter walk test, and during sleep. At the hospital and at the follow-ups patients are asked to rate their pain at rest and during a 5-meter walk test.

Use of rescue-analgesics (opioids) or other specific pain-relieving actions that differ from standard treatment is noted in the CRF.

The presence of dysesthesia or other side effects will be evaluated at each follow-up.

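### The added LA-response analysis in 7.2 is not a randomised contrast; taken alone, it mixes any cryo effect with the prognostic value of LA relief

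*Combined protocol and SAP*

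**What the plan says.** Section 7.2 plans by-arm ITT and PP analyses of the primary and secondary outcomes. For the secondary outcomes it then adds an analysis by "pain relief during the initial LA injection in the cryo group versus the remaining patients from both groups". The rule that follows, a P-value below "0.05 is considered significant", applies to all tests. The added analysis is not called exploratory, and no interaction test is named. The section also promises a "complete statistical analysis plan submitted to publication".

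Three other sections bear on what LA relief means and when it is known:

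- Section 3.2 lists, as a secondary outcome, the change in walk-test VAS around the blockade.
- Section 8.2.2 says that 5–15 minutes after the injection "the effect is evaluated by assessing pain in the surgical area and asking the patient whether there is a pain relief". Freezing comes next ("Following this evaluation, cryoneurolysis"). For sham: "The exact same procedure as in the cryo-group is performed, except that the nerves are not frozen with the cryoneurolysis apparatus".
- Section 8.3 says "Pain is rated by the patient before the intervention, after the initial LA injection, at home on days 2-7" and at later follow-ups, and that "At the hospital and at the follow-ups patients are asked to rate their pain at rest and during a 5-meter walk test".

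**The concern.** On the natural reading, one group consists only of cryo patients with LA relief. The other combines cryo patients without relief and every sham patient, with or without relief. The groups therefore differ in both treatment and LA response. If patients who respond to the block tend to have more or less pain later for reasons unrelated to freezing, that difference enters the contrast as though it were a cryo effect. The comparator also contains frozen patients, so a real effect is diluted if non-responders benefit too.

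At stake is a claim that LA response identifies who benefits from cryoneurolysis. A significant result from this contrast alone could mean that freezing helps responders, that it helps everyone, or that responders simply do better.

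**Working it through.** **Inputs from the protocol.** 22 per arm (4.2). Mean 390, SD 208 and a relevant reduction of 50%, so 0.5 × 390 = 195 points; two-sided 0.05 (7.1). The 195 and 208 belong to the primary outcome and are borrowed only for scale.

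**Assumptions.** Responder share p = 30/50/70% in both arms (about 7, 11 or 15 of 22); difference D between responders and non-responders regardless of treatment; normal outcome. The documents give neither p nor D.

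**The plan's own figure.** 2 × (1.960 + 0.8416)² × (208/195)² = 17.86, so 18 per group, as in 7.1. With 22 per group, t-test power is 86%. The plan gives no figure for the LA-response analysis.

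**Composition of the two sets.**
- Selected set: 22p cryo patients, all responders.
- Comparator: 22(1−p) cryo non-responders plus 22 sham patients, in total 22(2−p).
- Responder share in the comparator: p/(2−p). Frozen share: (1−p)/(2−p).

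**No cryo effect.** The expected difference is D × [1 − p/(2−p)] = D × (2−2p)/(2−p). The multiplier is 1.4/1.7 = 0.82, 1.0/1.5 = 0.67 and 0.6/1.3 = 0.46 for p = 30/50/70%. Rejection rates at P<0.05 from 40,000 simulated trials per cell, with SD 1 within response strata:

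| D (SD) | p = 30% | p = 50% | p = 70% |
|---|---|---|---|
| 0 | 5.1% | 5.1% | 5.2% |
| 0.3 | 8.5% | 8.5% | 6.9% |
| 0.5 | 15.1% | 14.4% | 10.2% |
| −0.5 | 15.1% | 14.2% | 10.2% |

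At −0.5 SD nearly all rejections go against cryo. Holding the total SD at 1 instead changes the 0.5 SD row little (15.5/15.0/10.7%). Cryo versus sham within responders stays at 4.7–5.2% throughout, and the arm-by-response interaction at 4.8–5.2%.

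**Real effect of τ = 195 points, D = 0.**
- Equal benefit in everyone: the contrast estimates τ/(2−p), that is 195/1.7 = 115, 195/1.5 = 130 and 195/1.3 = 150 points. Power is 20/37/56%, against 86% for the by-arm test.
- Benefit in responders only: it estimates the full 195 points, with power 57/74/82%. Cryo versus sham within responders has 32/54/70% when stratum sizes vary at random.

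**A randomised comparator exists.** Both arms receive the LA injection (4.1), sham follows the same steps, and relief is checked before freezing (8.2.2). LA response can therefore be treated as a variable that precedes freezing in both arms, and cryo versus sham within a response stratum remains a randomised comparison.

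**The case against.** **The sentence is loosely worded.** It names neither a responder group nor a test. This stands in part. A reader might infer that LA relief is wholly undefined, which goes too far: 3.2 gives a measure and 8.2.2 a yes/no question. What is missing is the choice between them and a cut-off. But any split of part of the cryo group against the rest of both groups selects on arm and LA response together, so looseness does not rescue the contrast.

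**Other text in 7.2 may cover it.** The section allows univariate or multivariate analyses where appropriate and promises a complete analysis plan. The former commits to no interaction test. The latter is where the correction can be made, but it does not make it.

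**The harm is hypothetical.** This stands as to size and direction. With D = 0 there is no inflation, and nothing in the documents fixes D. The simulation covers continuous, normal outcomes only, not re-admission or mortality, and not outcomes likely to be skewed, such as length of stay and opioid use.

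**The planned contrast can have more power.** True if only responders benefit and relief is not prognostic (74% against 54% at p = 50%). The documents support neither condition.

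**Two stronger readings fail.**
- A reader might infer that the contrast gives the same answer whether only responders benefit or everyone does and relief is prognostic. With equal benefit it estimates [τ + D(2−2p)]/(2−p), which equals τ only when D = τ/2 = 97.5 points, or 97.5/208 = 0.47 SD. At 0.25 SD (52 points) it gives about 158/165/174, and at 1.0 SD (208 points) about 286/269/246.
- A reader might infer that the competing explanations cannot be separated at all. The by-arm results are reported alongside. Their expectation is p × 195 = 59/98/137 points if only responders benefit, 195 if everyone does, and 0 if responders merely do better. That helps interpretation, though imprecisely with 22 per arm.

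**Conclusion.** The point holds and should be corrected before unblinding. The added analysis is not a randomised contrast. Taken alone, it mixes a cryo effect with any prognostic value of LA relief, and it dilutes a real effect if non-responders also benefit. That much follows from the composition of the groups, on the natural reading of the sentence. The size does not: false-positive rates of about 5% at D = 0, 7–9% at 0.3 SD and 10–15% at 0.5 SD rest on assumed values of p and D, and the sign of D is unknown.

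A reader might infer that the trial's main conclusions are at risk. The documents do not support that. The analysis is additional and confined to the secondary outcomes; the primary endpoint, the sample size and the by-arm ITT and PP analyses are untouched.

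**What to change.** Replace the sentence in 7.2 with:

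> Exploratory: LA response is the change in patient-rated VAS from before the LA injection to the rating after LA and before freezing or sham, obtained in the same way in both arms (walk-test VAS if it is rated at that point, otherwise the rating that is taken then). Effect modification is assessed by the arm-by-LA-response interaction, adjusted for pre-LA VAS. Cryo versus sham differences with 95% CIs are reported within responders and non-responders, using one threshold fixed before unblinding; significance in one stratum only is not evidence of effect modification. The change in VAS around the blockade is not itself analysed as an outcome in this analysis.

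For dichotomous outcomes, report counts by arm and stratum. The last sentence of the replacement is needed because 3.2 lists that change as a secondary outcome and it now becomes the moderator.

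Sections 3.2, 8.2.2 and 8.3 must be reconciled on which rating is taken after LA and before freezing. A reader might infer that the fix needs no new data. That is not established: 8.2.2 describes a check without naming a walk test, and 8.3 plans in-hospital walk-test ratings without placing one at that point. The wording above allows for either case.

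The cost is a few sentences of text and low precision. Borrowing 195 points and SD 208:

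- Within responders at 7/11/15 per group, power is about 37/55/70%, with 95% CI half-widths of about 242/185/156 points. The 37% at 7 per group differs from the 32% above because stratum sizes are fixed here.
- The dichotomised interaction has about 29/33/29% power, with half-widths of about 272/253/272 points.
- The one-stratum caution matters. With equal benefit in everyone and strata of 7 and 15 per arm, exactly one stratum is significant with probability 0.365 × 0.302 + 0.635 × 0.698 = 0.55; with 11 and 11 it is 2 × 0.553 × 0.447 = 0.49.

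If only responders benefit and relief is not prognostic, the replacement has less power than the planned contrast. The result can only be exploratory.
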